#### **7.3.5. Calculation details for sensitivity analysis including suspected HZ cases captured in the gap between primary and ZOSTER-049 study**

*The following positive rates of confirmed cases out of the suspected cases are assumed in this sensitivity analysis: 30%, 40% and 50%. The selection of those positive rates considers the true positive rate from clinically evaluated suspected cases on the HZ/su cohorts from study ZOSTER-006, ZOSTER-022 and ZOSTER-049, which are 13%, 35% and 39% respectively. Please note that the actual positive rate based on self-*

*reported suspected cases is expected to be lower than what is based on clinically evaluated suspected cases. Therefore, these selected positive rates are conservatively high and would be able to adequately assess the possible influence on VE.*

*The following simulation considering 30% confirmation rate is planned to account for the uncertainties around which suspected subjects could have been positive and what is their respective follow-up times:*

1. *Assume p=30%, the number of confirmed cases is denoted as n which equals N\*30%, where N is the total # of subjects who self-reported HZ case during the gap period.*
2. *Randomly draw n subjects from N. For each drawn subject, their follow-up time is simulated from a uniform distribution (0, GT] where GT is the actual time that subject had during the gap period.*
3. *Update the follow-up time for each of the n subjects with the simulated follow-up time*
4. *Data from those n subjects are excluded from ZOSTER-049 data.*
5. *Following the same steps in VE analysis B to calculate VE with the updated total number of confirmed cases and updated total follow-up time. Obtain the results for each round of simulation*
6. *Repeat step 2-5 for 100 times.*
7. *Calculate and present mean, min, max, Q1 and Q3 of VEs obtained by the 100 simulations*

*Repeat Step 1 through 7 to derive the VE results using other two assumed p=40% and 50%.*

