The primary analysis (A) will assess the VE during this study and will use the historical control estimates adjusted for region and age categories at randomization/vaccination during the ZOSTER-006/022 studies. Vaccine effects will be estimated by calculating the VE and estimating 95% CIs based on the variance of the observed population in this study and treating the historical control as constant, similarly, as described in [Morrison, 2015]. The secondary analysis C in [Table 1](#) will assess the VE over each year of follow-up, similarly to what is planned in analysis A.

See Section [7.3](#) for more details on the vaccine efficacy methodology.

The purpose of these analyses will be descriptive and therefore the CIs will not be adjusted for multiple testing.

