#### 6.2.2.2. **Sensitivity analysis including suspected HZ cases captured in the gap between primary studies and ZOSTER-049 study.**

*In the current calculation of VE for study ZOSTER-049, the suspected HZ cases during the time between the last visit of studies ZOSTER-006/022 and initiation of study ZOSTER-049 (the “gap period”) is not considered as confirmed cases. Per CHMP recommendation, a sensitivity analysis on the primary VE analysis during the entire follow-up period since ZOSTER-006/022 is planned to include potentially confirmed HZ cases during this gap period (Analysis B on mTVC-pooled ZOSTER-006/022 and mTVC-LTFU and Control group).*

*It is known that there are some self-reported suspected cases of HZ during the gap period, but these cases were not able to be confirmed as per the study protocol requirements, hence the true number of confirmed cases is unknown. The planned sensitivity analysis will assume different, yet conservatively high positive rates on the self-reported suspected cases to adequately assess the impact due to potentially confirmed cases. Please refer to Section 7.3.5 for more details*

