For the clinical endpoint linked to a **confirmation of HZ**, since there is no possibility to confirm a suspected HZ case during the gap, the follow-up time for subjects who came back to ZOSTER-049 will be computed minus the gap between the end of study efficacy cut-off date (21 April 2015) of ZOSTER-006/022 and the first visit for each subject **in ZOSTER-049**.

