***To note - North America is used as reference group***

2. Determine the Age adjusted historical control rate:

Using the coefficients from the Poisson regression in (1), the age-specific HZ incidence rates for an age stratum for Placebo group will be calculated as:

$$\text{Age specific } r_{\text{HZhistorical control reference group}} = \exp(\alpha + \beta_{\text{Australasia}} * \text{Region_Australasia} + \beta_{\text{Europe}} * \text{Region_Europe} + \beta_{\text{Latin America}} * \text{Region_Latin America})$$

Once the age-specific incidence rates are calculated for the historical control data from the ZOSTER-006 and ZOSTER-022, the results will be used to calculate age-specific controls rates on the hypothetical control group for the ZOSTER-049 interim and final analyses.

3. Determine the number of HZ cases for the age adjusted historical controls:

For each scheduled analysis, the age-specific follow-up time observed in ZOSTER-049 will be used as the follow-up time on the corresponding age-specific hypothetical control on ZOSTER-049. The total number of subject-years of HZ surveillance ( $F_{\text{Age}}$ ) for each age-strata will be then multiplied by the age-specific incidence rate that was estimated from step 2, to obtain the expected number of evaluable cases of HZ ( $n_{\text{Age}}$ ) for a specific age strata in the hypothetical control in ZOSTER-049:

$$n_{\text{Age}} = F_{\text{Age}} * \exp(\alpha + \beta_{\text{Australasia}} * \text{RegionAustralasia} + \beta_{\text{Europe}} * \text{RegionEurope} + \beta_{\text{Latin America}} * \text{RegionLatin America})$$

Once the expected number of cases for the hypothetical controls are determined for each age strata, expected HZ incidence rate for the hypothetical controls will be calculated by summing the numbers of expected evaluable cases of HZ for each age strata, and dividing by the total number of subject-years of HZ surveillance among all subjects during the ZOSTER-049 study.

*For the overall calculation of VE starting from the ZOSTER-006/022 study, the observed incidence rate for Placebo during ZOSTER-006/022 and the predicted incidence rate during ZOSTER-049 will be used in the calculation.*

*In the situation that there are very few subjects during the last year of follow-up with limited total follow-up time, data from both year 11 and year 12 will be pooled in the VE analysis.*

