#### **7.3.4. Method for computing VE and the associated CIs**

Once estimated data for the hypothetical control are generated as per steps listed in Section 7.3.2, following similar approach in ZOSTER-006/022, Poisson regression model will be used to estimate VEs and the associated CIs for all the planned VE analysis. Region will be included as a fixed effect and analysis will be performed on the following age strata ((50-59, 60-69, 70-79, ≥80, ≥60, ≥70 YOA) separately and overall.

*In the situation that there is no case in HZ/su group and >0 cases in Placebo group, VE and UL of VE will be set to be 100%. In the situation that there is >0 cases in HZ/su group and 0 case in Placebo group, VE and CI of VE will be set as “not available” (“-” or “U”).*

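### The gap-period sensitivity analysis of Analysis B counts gap HZ cases but gives gap person-time only to those cases, so VE is too low for any given number of counted cases

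*SAP*

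**What the plan says.** For endpoints that need confirmed HZ, SAP 7.3.1 notes that a suspected case could not be confirmed between the studies, so follow-up for returning subjects "will be computed minus the gap between the end of study efficacy cut-off date (21 April 2015) of ZOSTER-006/022 and the first visit". The main Analysis B thus has no gap cases and no gap time, which is consistent.

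SAP 7.3.5 details the sensitivity analysis that SAP 6.2.2.2 attributes to a CHMP recommendation:

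- Step 1: n = p x N, where N is the number of subjects who self-reported HZ in the gap.
- Step 2: n of the N are drawn at random. Each gets a time uniform on (0, GT], where GT is that subject's own time in the gap.
- Step 3: "Update the follow-up time for each of the n subjects with the simulated follow-up time".
- Step 4: the ZOSTER-049 data of the drawn subjects are dropped, in line with the first-event rule.
- Step 5: Analysis B is rerun on the new totals.
- Steps 6 and 7: after 100 repeats, "Calculate and present mean, min, max, Q1 and Q3 of VEs obtained by the 100 simulations".

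On the control side, SAP 7.3.3 says that "the observed incidence rate for Placebo during ZOSTER-006/022 and the predicted incidence rate during ZOSTER-049 will be used in the calculation". It sets the hypothetical control's follow-up in ZOSTER-049 equal to that of the vaccinees, so no expected control cases arise in the gap. For the primary analysis, SAP 6.2.1 describes "treating the historical control as constant". SAP 7.3.4 says that a "Poisson regression model will be used to estimate VEs and the associated CIs for all the planned VE analysis".

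The SAP calls this analysis conservative only because the assumed positive rates (30%, 40%, 50%) are high against the 13%, 35% and 39% seen in clinically evaluated suspected cases. It does not mention person-time.

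**The concern.** A rate needs events and time at risk from the same period. Here the gap supplies events, but only the subjects with a drawn event supply gap time. Every other returning HZ/su recipient was also at risk in the gap, including the N - n self-reporters who are not drawn, and contributes nothing. The HZ/su rate rises, and VE falls, even if the vaccine protected exactly as well in the gap as before and after it.

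The purpose of the analysis is to show how gap cases affect VE since ZOSTER-006/022. As written, part of any reported fall would be due to the missing person-time, and the reader could not separate that part from the effect of the gap cases.

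**Working it through.** **1. The plan's own figure.** Protocol 11.4 expects 6406 returning evaluable subjects: 7344 x 0.50 = 3672, plus 6075 x 0.45 = 2733.75, total 6405.75. This reproduces. Protocol 11.4.1 then works with about 6000.

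**2. Person-years in Analysis B.** Primary studies: (7344 + 6075) = 13,419 vaccinees x about 4 y (Protocol 1.2.1) = 53,676. ZOSTER-049: 6000 x 6 y = 36,000. Total 89,676.

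**3. Omitted gap time.** The documents give no distribution of gap lengths. As an assumption, I take 21 April 2015 to the two first-visit dates in the SAP 6.3.3 worked example:

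- 2 February 2016: 287/365.25 = 0.79 y; x 6000 = 4715 person-years
- 5 July 2016: 441/365.25 = 1.21 y; x 6000 = 7244 person-years

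As a share g of 89,676, this is 5.26% to 8.08%.

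**4. Null check.** VE = 1 - (HZ/su rate / control rate). If the gap rate equals the rate elsewhere and all gap cases are counted, true VE does not change. The plan raises the case count by a factor of about 1 + g and leaves person-time almost unchanged, so the spurious loss is about (1 - VE) x g:

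| VE | g = 5.26% | g = 8.08% |
|---|---|---|
| 90% | 0.5 points | 0.8 points |
| 80% | 1.1 | 1.6 |
| 65% | 1.8 | 2.8 |

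The 80% and 65% values come from the titles of the protocol's power tables; 90% is assumed. If attrition cuts mean ZOSTER-049 follow-up to 4.5 y (assumed), the total is 80,676 person-years and the losses are 0.6-0.9, 1.2-1.8 and 2.0-3.1 points.

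**5. Full steps 2 to 4.** Take VE 80%, control rate 10 per 1000 (upper value in Protocol 1.1) and gap 1.21 y. Base cases: 89,676 x 0.002 = 179.4. Gap cases: 7244 x 0.002 = 14.5. Each drawn case loses 6 y and gains on average 0.60 y.

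- As written: 193.8 / 89,598 person-years, VE 78.37%.
- With gap time for the other 5985.5 returning subjects: 193.8 / 96,825, VE 79.98%.

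Adding gap time to the control alone leaves VE at 78.37% (a change below 0.001 points). Reading step 3 as replacing, not adding to, the ZOSTER-006/022 follow-up lowers VE by only a further 0.001-0.04 points.

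**6. An illustration with more cases.** Same inputs, assumed N = 60 and p = 50%, so n = 30.

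- As written: 209.4 / (89,676 - 180 + 18) = 209.4 / 89,514, VE 76.6%.
- Matched: 209.4 / (89,514 + 5970 x 1.207) = 209.4 / 96,722, VE 78.4%.

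The loss is 3.4 points as written and 1.6 matched.

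**7. Incomplete capture.** Let a share s of true gap cases be counted, with an equal gap rate. As written, 1 - VE is too high by a factor 1 + sg. Matched, it is too low by a factor (1 + sg)/(1 + g). At VE 80% and g = 8.08%:

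- s = 0.8: errors of -1.3 (as written) and +0.3 points (matched).
- s = 0.3: -0.5 and +1.0.

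The two are equally far from the truth at s = 1/(2 + g), about 0.48-0.49. If instead the gap rate is twice the rate elsewhere and s = 0.3, true VE is 1 - 0.2 x 1.1616/1.0808 = 78.5%, while the as-written VE is 1 - 0.2 x 1.0485 = 79.0%.

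**8. Step 7 spread.** In six assumed scenarios (N 30-120, p 30-50%, VE 65-90%, control 5-10 per 1000), the min-max of overall VE over 100 rounds is 0.002-0.03 points. The exact Poisson 95% CI with the control held constant is 4.3-8.6 points wide. In an assumed small age stratum (10% of person-time, 6 of 60 reporters, p = 50%) the min-max is about 5.6 points.

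**The case against.** The strongest counter-argument is that SAP 7.3.1 removes gap time for a good reason: nobody was under surveillance. Gap cases are self-reported, and in the words of SAP 6.2.2.2, "hence the true number of confirmed cases is unknown". Giving each non-reporter a full event-free gap assumes that the history taken at entry (Protocol 6.5.3) caught every case. If it did not, the matched version errs in favour of the vaccine and could even show VE above the main Analysis B. This stands. It is why both versions are needed and why neither is simply the correct one.

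A reader might infer that the planned analysis always overstates the VE loss, or that it gives a lower bound for VE. The documents support neither. The statement holds for a given number of counted cases. The doubled-rate example in step 7 of the working puts the as-written VE above the truth, and no document gives the capture share or the gap rate.

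A reader might also fault the simulation summary for understating uncertainty. But SAP 7.3.5 says the simulation is "planned to account for the uncertainties around which suspected subjects could have been positive", together with their follow-up times. The spread shows that, and SAP 7.3.4 already provides CIs. Only a label is missing. Averaging the CI limits over rounds would not give a valid combined interval.

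The remaining objection is size: at VE 80-90% the shift of 0.5-1.6 points lies inside the width of the CI. That is true and limits the weight of the point, but it does not make cases and time match.

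**Conclusion.** The mismatch is real on the text: gap cases enter and gap time does not, except for the drawn cases themselves. For any given number of counted gap cases, VE is too low. With an equal gap rate and full capture, the spurious loss is about 0.5-0.8 points at VE 90%, 1.1-1.6 at 80% and 1.8-2.8 at 65%. These figures rest on planning numbers and an assumed gap of 0.79-1.21 y; N, the actual gap lengths and the placebo rate are not in the documents. Incomplete self-report works against this bias and can outweigh it.

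The consequence is modest. One descriptive sensitivity analysis, overall and by age stratum, is affected; Analysis A is not. The plan should still be changed, because the declared conservatism lies only in the positive rates and this second effect is not disclosed.

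**What to change.** - **Step 3:** say that the simulated gap time is added to each drawn subject's ZOSTER-006/022 follow-up. In a second, matched version, also add the full gap time for every other returning subject without an earlier confirmed HZ case.
- **Definition of GT:** use the SAP 7.3.1 interval, from 21 April 2015 to the first ZOSTER-049 visit. SAP 6.2.2.2 starts the gap at the last ZOSTER-006/022 visit, and the two must be reconciled.
- **Step 5:** let the control cover the same period in the matched version. This is for consistency only; the effect on VE is negligible.
- **Presentation:** show the matched version beside the one now written. State that the matched version assumes self-report captured the gap cases and overstates VE if it did not. Do not label the as-written version a lower bound: that holds only under conditions such as a gap HZ rate no higher than elsewhere.
- **Step 7:** add a note that the min-max and quartiles describe the random draw of cases and event times, not sampling error, and that the CIs of SAP 7.3.4 apply.

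The cost is a few lines of SAP text, a small change to one program and one more set of table rows. No new data are needed, because SAP 6.1.1 already derives the interval from cut-off to first visit.

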### 7.3.6. Calculation details for sensitivity analysis considering subjects aging when enrolled into ZOSTER-049 from ZOSTER-006/-022

*Please see below for the illustration on the implementation steps to perform this VE sensitivity analysis by age strata:*

ZOSTER-006/022 control		ZOSTER-049 hypothetical control (estimated HZ cases to be used in 049 VE analysis)				
Age group	IR estimate	Age group	N (ZOSTER-049)	FU Time (FT) (ZOSTER-049)	IR estimate Based on ZOSTER-006/022 control	HZ case
50-54 YOA (at primary vaccination )	IR1	50-54 YOA (at Z-049 enrollment )	NA	NA	NA	NA

## CONFIDENTIAL

201190 (ZOSTER-049 EXT:006-022)  
Statistical Analysis Plan Amendment 3

ZOSTER-006/022 control		ZOSTER-049 hypothetical control (estimated HZ cases to be used in 049 VE analysis)				
55-59 YOA (at primary vaccination )	IR2	55-59 YOA (at Z-049 enrollment)	N1	FT_1	IR2	$n1=FT1*IR2$
60-64 YOA (at primary vaccination )	IR3	60-64 YOA (at Z-049 enrollment)	N2	FT_2	IR3	$n2=FT2*IR3$
65-69 YOA (at primary vaccination )	IR4	65-69 YOA (at Z-049 enrollment)	N3	FT_3	IR4	$n3=FT3*IR4$
70-74 YOA (at primary vaccination )	IR5	70-74 YOA (at Z-049 enrollment)	N4	FT_4	IR5	$n4=FT4*IR5$
75-79 YOA (at primary vaccination )	IR6	75-79 YOA (at Z-049 enrollment)	N5	FT_5	IR6	$n5=FT5*IR6$
80-84 YOA (at primary vaccination )	IR7	80-84 YOA (at primary vaccination)	N6	FT_6	IR7	$n6=FT6*IR7$
>=85 YOA (at primary vaccination )	IR8	>=85 YOA (at Z-049 Enrollment)	N7	FT_7	IR8	$n7=FT7*IR8$

The resulting HZ cases for age strata defined by subjects' age at first vaccination in ZOSTER-006/022 studies are then calculated in the following way which are to be used in the VE sensitivity analysis by strata following the same methodology used in VE Analysis A, B and C:

HZ cases for 50-59 YOA:  $n1+n2$

HZ cases for 60-69 YOA:  $n3+n4$

HZ cases for 70-79 YOA:  $n5+n6$

HZ cases for >=80 YOA:  $n7$

Since all subjects in ZOSTER-049 study were  $\geq 55$  YOA at their enrollment, for the overall VE sensitivity analysis, subjects who were 50-54 YOA at primary vaccination were excluded from the ZOSTER-006/022 Placebo group when building the

*hypothetical control. The estimated IR are then multiplied by the total follow-up time observed in ZOSTER-049 study to obtain the estimated HZ cases, which will be subsequently used to calculate overall VE following the same methodology used in VE Analysis A, B and C.*

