#### 6.2.2.3. **Sensitivity analysis considering subjects aging when enrolled into ZOSTER-049 from ZOSTER-006/022**

*Since all subjects enrolled in ZOSTER-049 study had aged for ~5 years compared to when they were enrolled in ZOSTER-006/022 studies, a sensitivity analysis on VE (analysis A, B and C on mTVC - LTFU and Control group only.) is planned to consider the aging factor on ZOSTER-049 subjects when utilizing the historical control to estimate the incident rate on the hypothetical control in ZOSTER-049 study. Please refer to Section 7.3.6 for more details*

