*For the sensitivity analysis considering subjects aging when enrolled into ZOSTER-049 from ZOSTER-006/022. The same step 1,2 and 3 will be used to calculate the incidence rates on ZOSTER-049 historical control using data from ZOSTER-006/022 control. The only difference is that estimated incidence rates will be applied to the age-specific group based on the approximate age in years when the subjects were enrolled in the beginning of study ZOSTER-049 to estimate the HZ cases in the hypothetical control.*

*For the VE analysis for PHN or HZ related complication (other than PHN) the same poison regression models detailed in step 1, 2 and 3 will be used to generate the hypothetical controls for the incidence of PHN or HZ related complication (other than PHN) in study ZOSTER-049.*

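### SAP 7.3.6: the 80-84 row of the hypothetical control is labelled by age at primary vaccination; coded as printed, it would give a wrong expected case count for the 70-79 stratum of the ageing sensitivity analysis

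*SAP*

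**What the plan says.** SAP 6.2.2.3 plans a sensitivity analysis of vaccine efficacy (VE), for Analyses A, B and C, because "all subjects enrolled in ZOSTER-049 study had aged for ~5 years compared to when they were enrolled in ZOSTER-006/022 studies". SAP 7.3.3 gives the rule: incidence rates estimated from the ZOSTER-006/022 placebo group are "applied to the age-specific group based on the approximate age in years when the subjects were enrolled in the beginning of study ZOSTER-049".

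SAP 7.3.6 turns this into a table. The left half lists placebo rates IR1 to IR8 by age at primary vaccination. The right half lists, for the hypothetical control, an age band, the number of subjects N, the follow-up FT and the expected cases n. The last three rows of the right half are:

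- n5 = FT_5 × IR6, labelled "75-79 YOA (at Z-049 enrollment")
- n6 = FT_6 × IR7, labelled "80-84 YOA (at primary vaccination")
- n7 = FT_7 × IR8, labelled ">=85 YOA (at Z-049 Enrollment")

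Below the table, expected cases are returned to strata of age at first vaccination: "HZ cases for 70-79 YOA" is n5+n6, and "HZ cases for >=80 YOA" is n7. N, FT and IR are symbols throughout, with no values.

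**The concern.** The n6 row is the only one in the right half that is not defined by enrolment age. The section presents the table as the steps for implementation, so a programmer could reasonably code it cell by cell. Doing so would place one group of subjects in two rows and leave another group out. The expected cases credited to the 70-79 stratum would then come partly from people who were not 70-79 at vaccination. The analysis is meant to show whether VE holds up once ageing is allowed for, and the error would fall in one of its older strata.

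**Working it through.** There is no stated figure to reproduce. The check is on band membership and algebra, followed by an illustration.

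**Inputs from the documents.** Ageing of about 5 years (SAP 6.2.2.3). First-visit windows starting at 3.5 years after dose 2, with an example at 4.26 years (SAP 6.3.3). Row labels and mapping (SAP 7.3.6). Incidence of about 10 per 1000 person-years at 60 and over (Protocol 1.1). 2734 subjects expected from ZOSTER-022, the study in people aged 70 and over (Protocol 11.4). About 6 years of follow-up (Protocol 3). VE of 80% and 65%, as in the titles of Protocol Tables 29 and 30.

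**Assumptions.** The age mix within those aged 70 and over, and the rates by band.

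**Step 1: who falls where, with a 5-year shift.**

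| Age at vaccination | Age at enrolment | Row intended | Row as printed |
|---|---|---|---|
| 70-74 | 75-79 | 5 | 5 |
| 75-79 | 80-84 | 6 | none |
| 80-84 | 85-89 | 7 | 6 and 7 |
| >=85 | >=90 | 7 | 7 |

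With a shift of s years and ages spread evenly within the band, the share of those aged 80-84 at vaccination who are also 85 or older at enrolment is s/5, capped at 1. This gives 80% at 4 years, 90% at 4.5 and 100% from 5 upward. The same share of those aged 80-84 at enrolment falls in no row.

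**Step 2: algebra for the 70-79 stratum.** Let a, b and c be the ZOSTER-049 follow-up of subjects aged 70-74, 75-79 and 80-84 at vaccination.

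- Intended: n5+n6 = a·IR6 + b·IR7
- As printed: n5+n6 = a·IR6 + c·IR7

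If the control denominator is the stratum's own follow-up (a+b), as step 3 of SAP 7.3.3 implies, then reported VE = 1 − (1 − true VE) × intended/printed.

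**Step 3: illustration for Analysis A, true VE 80%, IR6 = 10 per 1000.**

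| Assumed a/b/c (% of 70+ follow-up) | IR7 per 1000 | Printed/intended | Reported VE |
|---|---|---|---|
| 50/30/15 | 10 | 650/800 = 0.81 | 75.4% |
| 50/30/15 | 11 | 665/830 = 0.80 | 75.0% |
| 55/28/13 | 10 | 680/830 = 0.82 | 75.6% |
| 55/28/13 | 11 | 693/858 = 0.81 | 75.2% |
| 45/33/16 | 10 | 610/780 = 0.78 | 74.4% |
| 45/33/16 | 11 | 626/813 = 0.77 | 74.0% |

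In cases, take a 45/33/17/5 split (the last share being >=85), 2734 subjects, 6 years and 10 per 1000 in every band. Follow-up is then 7382, 5413, 2789 and 820 person-years. Expected cases for 70-79 are 73.8 + 54.1 = 128.0 as intended and 73.8 + 27.9 = 101.7 as printed. A true VE of 80% becomes 74.8%, and 65% becomes 56.0%.

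**Step 4: does the direction hold?** With true VE 80%, a/b from 1 to 2 and IR7/IR6 from 0.8 to 1.2:

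| c/b | Reported VE, denominator a+b |
|---|---|
| 0.25 | 66.2-74.5% |
| 0.50 | 72.5-76.7% |
| 0.75 | 76.8-78.5% |
| 1.00 | 80.0% |
| 1.25 | 81.3-82.4% |

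If the control denominator were instead FT_5+FT_6 as labelled (a+c), reported VE = 1 − (1 − true VE) × [intended/(a+b)] / [printed/(a+c)]. Over the same grid this gives 78.8-81.2%, and exactly 80% when IR6 = IR7.

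**Step 5: where n6 enters.** It enters the 70-79 stratum. It would also enter >=60 and >=70, which SAP Table 1 lists for all three analyses, if those are formed by adding the n's; SAP 7.3.6 gives no formula for them. The >=80 stratum uses n7 only. The overall ageing-sensitivity estimate multiplies the estimated incidence by total follow-up and does not sum n1 to n7.

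**The case against.** The strongest reply is that the SAP settles the matter itself. SAP 7.3.3 states the enrolment-age rule for the whole analysis, every neighbouring row follows it, and the two mapping lines make sense only if the n6 row is 80-84 at enrolment. The cell is therefore most likely a labelling slip, and nothing shows that the programs follow it. All of that stands. It does not remove the need to correct a cell in what the SAP offers as implementation steps.

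A reader might go further and infer that the plan double-counts a band and that VE for 70-79 is understated. The documents do not support that. Any error arises only if the cell is coded literally. The duplication is complete only for a shift of 5 years or more, and SAP 6.3.3 allows for shorter ones. Understatement needs less follow-up in those aged 80-84 than in those aged 75-79 at vaccination, which is plausible but not given. It also needs a control denominator equal to the stratum's own follow-up, which is the natural reading but is not spelled out for this analysis.

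Nor do the illustrative shifts carry over to the other analyses. Analysis B combines observed ZOSTER-006/022 placebo incidence with the predicted rate, which dilutes any error. In Analysis C, results from the pooled ZOSTER-006/022 studies are presented by those studies' own methods. The whole exercise is descriptive, with no success criteria (SAP 3).

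**Conclusion.** The label is wrong as printed and contradicts the SAP's own rule and mapping. Literal coding would give a wrong expected control count for the 70-79 stratum, except in the coincidental case of equal follow-up in the 75-79 and 80-84 bands. For Analysis A, VE would be understated if the denominator is the stratum's own follow-up and the 80-84 band contributes less follow-up than the 75-79 band: about 74-76% for a true 80% under the assumed mixes. With other follow-up patterns or another denominator it could be unchanged or overstated. The primary analysis is untouched. This is a narrow but real specification error, and the intended reading is clear.

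**What to change.** In the hypothetical-control half of the SAP 7.3.6 table, change the 80-84 label to *80-84 YOA (at Z-049 enrollment)* and take N6 and FT_6 from subjects in that band at enrolment. Confirm that the programs classify every row by enrolment age. State how >=60 and >=70 are formed.

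Add a check that FT_1 to FT_7 sum to total ZOSTER-049 follow-up. In the 45/33/17/5 illustration, literal coding would leave the sum short by 5413 − 2789 = 2624 person-years. Because the sum would agree by chance if those two bands had equal follow-up, also check that each subject falls in exactly one row.

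The cost is one table cell, a line or two of text and a short program check. No new data are needed.
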